### 3. GENERAL INFORMATION

Objective	To compare binocular visual outcomes with light adjustable lens (LAL) vs. Clareon monofocal/toric IOL when both are targeting mini-monovision (-0.75 ~ -1.00 D in the non-dominant eye).  The hypothesis is that the Clareon monofocal/toric IOL with mini-monovision will provide non-inferior binocular distance vision compared to LAL mini-monovision (non-inferiority margin: 0.1 logMAR).
Test Article(s)	The Clareon™ Monofocal Intraocular Lens (Toric and Non-Toric) The Light-Adjustable Lens™
Sample size	138 subjects total (69 in each group)
Study Population	Age-related Cataract patients with $\geq 0.75$ D corneal astigmatism and without previous experience of monovision $> -1.00$ D offset.
Number of sites	One
Study Design	Single center, multi-surgeon, prospective, randomized, comparative study.
Masking	None.
Variables	Primary: Binocular corrected distance visual acuity (CDVA), 3-months postop.  Secondary: 

• Binocular uncorrected distance visual acuity (UDVA), 3-months postop.

• Binocular distance-corrected intermediate visual acuity (DCIVA) at 66cm, 3-months postop.

• Binocular uncorrected intermediate visual acuity (UIVA) at 66cm, 3-months postop.

• Monocular corrected distance visual acuity (CDVA), 3-months postop.

- Monocular uncorrected distance visual acuity (UDVA), 3-months postop.
- Monocular distance-corrected intermediate visual acuity (DCIVA) at 66cm, 3-months postop.
- Monocular uncorrected intermediate visual acuity (UIVA) at 66cm, 3-months postop.

Exploratory:

- Binocular distance-corrected near visual acuity (DCNVA) at 40cm, 3-months postop.
- Binocular uncorrected near visual acuity (UNVA) at 40cm, 3-months postop.
- Monocular distance corrected defocus curve at 3 months post-op for both eyes in LAL group and dominant eye for Clareon group.
- Binocular defocus curve at 3 months post-op (dominant eye: plano corrected, non-dominant: -1.00D)
- Manifest refraction (MRSE, residual sphere, and residual astigmatism) at postoperative day 17-28 and at 3 months post-op.
- Patient reported spectacle usage questionnaire (PRSIQ) at postoperative day 17-28 and at 3 months post-op
- Total ocular, corneal and internal HOA and SA with iTRACE for both eyes in LAL group and dominant eye for Clareon group (Objective depth of focus measurement with iTRACE for each eyes in both groups)

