### 7.2. *Inclusion Criteria*

Subjects are eligible for the study if they meet the following criteria:

**Note:** Ocular criteria must be met in both eyes.

- Adult patients undergoing age-related cataract surgery with expected best-corrected visual outcomes of 20/25 or better
- Regular corneal astigmatism of 0.75D-2.50D
- Dilated pupil diameter of 7mm or greater

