## 8. STUDY DESIGN

### 8.1. ***Study Design***

This study is a single center, multi-surgeon, prospective, randomized, comparative study of binocular corrected distance visual acuity (CDVA) after successful bilateral cataract surgery. Subjects will be assessed pre-operatively, operatively and at up to 6 post-operative visits. Clinical evaluations will include administration of patient reported spectacle usage questionnaire (PRSIQ), as well as measurement of monocular and binocular visual acuities at distance, intermediate, and near, defocus curve, manifest refraction, measurement of higher order aberrations.

The primary outcome measure will be the binocular corrected distance visual acuity (CDVA), 3-months postop.

Secondary outcome measures are as follows:

- Binocular uncorrected distance visual acuity (UDVA), 3-months postop.
- Binocular distance-corrected intermediate visual acuity (DCIVA) at 66cm, 3-months postop.
- Binocular uncorrected intermediate visual acuity (UIVA) at 66cm, 3-months postop.
- Monocular corrected distance visual acuity (CDVA), 3-months postop.
- Monocular uncorrected distance visual acuity (UDVA), 3-months postop.

- Monocular distance-corrected intermediate visual acuity (DCIVA) at 66cm, 3-months postop.
- Monocular uncorrected intermediate visual acuity (UIVA) at 66cm, 3-months postop.

Exploratory outcome measures are as follows:

- Binocular distance-corrected near visual acuity (DCNVA) at 40cm, 3-months postop.
- Binocular uncorrected near visual acuity (UNVA) at 40cm, 3-months postop.
- Monocular distance corrected defocus curve at 3 months post-op for both eyes in LAL group and dominant eye for Clareon group.
- Binocular defocus curve at 3 months post-op (dominant eye: plano corrected, non-dominant: -1.00D)
- Manifest refraction (MRSE, residual sphere, and residual astigmatism) at postoperative day 17-28 and at 3 months post-op.
- Patient reported spectacle usage questionnaire (PRSIQ) at postoperative day 17-28 and at 3 months post-op
- Total ocular, corneal and internal HOA and SA with iTRACE for both eyes in LAL group and dominant eye for Clareon group (Objective depth of focus measurement with iTRACE for each eyes in both groups).
- Number of days and post-op office visits from cataract surgery to routine "release of care visit" (i.e. final lock-in for LAL group, 17-28 days after 2nd eye surgery for Clareon group).

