### ***8.3. Method of Assigning Subjects to Treatment Arms***

Subjects will be assigned to the Clareon monofocal or the LAL treatment groups in a 1:1 ratio using the method of randomly permuted blocks.

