##### **10.2.1. Within-treatment Changes**

For variables measured on a continuous scale, these summaries will include the sample size, as well as the mean, standard deviation, median, minimum, and maximum. For variables measured on a categorical scale, summaries will provide the number and percentage of eyes in each category. These summaries will be provided for all eyes completing the study.

Differences between parametric variables will be compared using a two-sample t-test. Differences between categorical variables will be compared using the 2-sample test for equality of proportions.

For non-inferiority testing, if the upper boundary of the 95th confidence interval is not greater than 0.1 logMAR, non-inferiority will be claimed.

The step-down methodology will be used on the non-inferiority endpoints in the following order:

- 1) Binocular CDVA
- 2) Binocular DCIVA
- 3) Binocular UDVA
- 4) Binocular UIVA

The correlation of total ocular and internal HOAs (especially SA) with monocular DCIVA will be evaluated using regression modelling. Findings from these models will provide an indication of whether any HOAs are statistically significantly associated with post-op DCIVA, and the strength of any such association.

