### **10.3. General Statistical Considerations**

The statistical analyses will be performed using R, version 4.2.2 or higher. Any statistical tests of hypotheses will employ a level of significance of alpha=0.05.

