## 15. STANDARD EVALUATION PROCEDURES

**Table 15.1. Proposed Visits and Study Assessments**

(visits are by patient, with both eyes tested)

Activity	Pre-operative	Operative	Postoperative					
	Visit 1	Visit 2a,2b	Visit 3	Visit 4	Visit 5	Visit 6	Visit 7	Visit 8
			POD 17-28	POD 24-42	POD 31-56	POD 38-63	POD 45-70	POD 90
Informed Consent	L,C							
Demographics	L,C							
General Information: Medical History	L,C							
Surgery		L,C						
Manifest refraction	L,C		L,C	L	L	L	L	L,C
Monocular uncorrected distance VA	L,C		L,C	L	L	L	L	L,C
Monocular corrected distance VA	L,C		L,C	L	L	L	L	L,C
Binocular uncorrected and best-corrected distance VA			L,C	L	L	L	L	L,C
Monocular uncorrected and best distance-corrected intermediate VA (66cm)			L,C	L	L	L	L	L,C
Binocular uncorrected and best distance-corrected intermediate VA (66cm)			L,C	L	L	L	L	L,C
Monocular uncorrected and best distance-corrected near VA (40cm)			L,C	L	L	L	L	L,C
Binocular uncorrected and best distance-corrected near VA (40cm)			L,C	L	L	L	L	L,C
Monocular Distance Corrected Defocus Curve								L,C
Binocular Defocus Curve (Dominant eye: plano corrected, non-dominant: -1.00D)								L,C
PRSIQ questionnaire			L,C					L,C
Total ocular, corneal and internal HOA and SA with iTRACE (Both eyes in LAL group and dominant eye for Clareon group)			L	L	L	L	L	L,C
Number of days and post-op office visits from cataract surgery to routine "release of care visit" (i.e. final lock-in for LAL group, 17-28 days after 2nd eye surgery for Clareon group)								L,C
Monitor for Adverse Events and Device Deficiencies		L,C	L,C	L,C	L,C	L,C	L,C	L,C
Complete Exit Form 								L,C

C = Clareon Group; L = LAL group

 Complete Exit Form upon termination of subject participation, or at Visit 8, whichever occurs first.

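### The 3-month acuity comparison ignores pre-operative acuity that is already collected: a modest, uncertain loss of precision, not an error

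*Combined protocol and SAP*

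**What the plan says.** Section 10.2.1 gives one method for comparing continuous outcomes between groups: "Differences between parametric variables will be compared using a two-sample t-test". The non-inferiority rule in the same section is that "if the upper boundary of the 95th confidence interval is not greater than 0.1 logMAR, non-inferiority will be claimed". It applies in step-down order to binocular CDVA, DCIVA, UDVA and UIVA. The section does not say which model the interval comes from; the t-test is the natural reading. The only regression it plans relates higher-order aberrations to monocular DCIVA. Section 10.3 adds: "Any statistical tests of hypotheses will employ a level of significance of alpha=0.05", without stating sidedness.

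Information available before surgery:

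- **Acuity.** Table 15.1 lists "Monocular corrected distance VA" at Visit 1 for both groups, with both eyes tested. Binocular distance acuity and all intermediate acuity start at Visit 3.
- **Corneal astigmatism.** Section 7.2 requires "Regular corneal astigmatism of 0.75D-2.50D" in both eyes. Table 15.1 has no row for it.
- **Surgeon.** Section 8.1 says: "This study is a single center, multi-surgeon, prospective, randomized, comparative study". Section 8.3 allocates "in a 1:1 ratio using the method of randomly permuted blocks" and names no stratification factor. The number of surgeons is not given, and surgeon is not listed as a recorded variable.

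**The concern.** A measurement taken before surgery that predicts the 3-month outcome can be put into a linear model. The model estimates the same treatment difference with less residual variance and accounts for chance imbalance in that measurement. Here the measurement is already scheduled, so a t-test that ignores it may give precision away.

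Precision has some value in this trial. Section 11 assumes a true difference of 0.05 logMAR, which uses half of the margin ("non-inferiority margin: 0.1 logMAR"), and says that the assumed difference and standard deviation are uncertain. The step-down order also means that a narrow miss on an early endpoint closes the later ones. What is at stake is interval width and a few points of power. The error rate of the test is not in question.

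**Working it through.** **Inputs.** From the documents: margin 0.10, true difference 0.05, SD 0.10, 69 per group (N=138), planned power 90%, alpha 0.05. Assumed, because the documents give no figure: the correlation r between the covariate and 3-month acuity, shown from 0 to 0.4.

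**Step 1: reproduce the plan's figure.** Unadjusted n per group = 2 × [SD × (z for alpha + z for power) / (margin − difference)]².

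- One-sided 0.05: 2 × [0.10 × (1.645 + 1.282) / 0.05]² = 68.5, so 69. This matches section 11.
- One-sided 0.025 (upper limit of a two-sided 95% interval): 2 × [0.10 × (1.960 + 1.282) / 0.05]² = 84.1, so 85. This does not match.

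**Step 2: unadjusted power at 69 per group.** The standard error is 0.10 × √(2/69) = 0.01703, so the noncentrality is 0.05 / 0.01703 = 2.937 on 136 degrees of freedom. The noncentral t gives 89.9% at one-sided 0.05 and 83.0% at one-sided 0.025.

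**Step 3: add one baseline covariate.** The residual SD becomes 0.10 × √(1 − r²). Estimating k covariate terms inflates the variance by about (N − 3)/(N − 3 − k), which is 135/134 for k=1, and leaves 135 degrees of freedom. For r=0.3 the effective SD is 0.10 × √0.91 × √(135/134) = 0.0957, and the noncentrality is 3.067.

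| Analysis | Power, one-sided 0.05 | Power, upper limit of two-sided 95% interval |
|---|---|---|
| t-test, no covariate | 89.9% | 83.0% |
| One covariate, r=0 | 89.7% | 82.8% |
| One covariate, r=0.2 | 90.8% | 84.3% |
| One covariate, r=0.3 | 92.0% | 86.1% |
| One covariate, r=0.4 | 93.7% | 88.7% |

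**Step 4: cost of further terms.** Adjustment breaks even where 1 − R² offsets the inflation, at R² of about k/135. That is 1/135 = 0.007 for one term (r about 0.09), 3/135 = 0.02 for three and 6/135 = 0.04 for six. If R² is zero, power at one-sided 0.05 falls from 89.9% to 89.3% with three terms or 88.7% with six. If baseline acuity has r=0.2 and the other terms add nothing, power at the two-sided 95% limit is 83.7% with three terms and 82.9% with six, against 83.0% unadjusted.

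**Step 5: compare with the sidedness question.** For 69 per group to give 90% power at one-sided 0.025, R² would have to be about 1 − 69/84.06 = 0.18, or r of about 0.42.

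**The case against.** The strongest reply is that nothing is broken. The trial was sized for an unadjusted comparison, which is valid under 1:1 randomisation and has its stated power at one-sided 0.05. Chance imbalance is already allowed for in the error rate. This stands, and it rules out calling the t-test a mistake.

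The second reply is that the gain could be nil for the primary endpoint, and this also stands. Pre-operative acuity is read through the cataract, while CDVA is read after its removal with refraction in place. Eligibility requires an expected 20/25 or better and excludes much ocular comorbidity, which narrows the outcome range. No step-down endpoint has a baseline of its own, so mean monocular CDVA is a proxy. A covariate need only be measured before treatment and be prognostic, but how prognostic it is here is unknown.

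A reader might go further and infer three things that the documents do not support:

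- *Adjustment can only help.* It does not in finite samples, as Step 4 shows.
- *Surgeon and corneal astigmatism are equally ready to use.* Neither is a scheduled study variable, and the number of surgeon terms is unknown. Astigmatism must be measured for eligibility and could bear on UDVA and UIVA, but section 9.2.2 treats it by toric lens, arcuate incision or light adjustment, so its remaining predictive value is not known.
- *The 83.0% is the price of not adjusting.* It comes from reading the interval as two-sided, which is a separate matter.

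A last reply is that the blinded re-estimation in section 11 already deals with uncertainty in the SD. It does so for the sample size, but it does not recover precision at a given size.

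**Conclusion.** The point holds as a modest efficiency suggestion. With one covariate the downside is about 0.2 points of power. At r=0.3 the gain is 2.1 points at one-sided 0.05 (89.9% to 92.0%) or 3.1 points at the two-sided 95% limit (83.0% to 86.1%). These figures rest on the plan's difference, SD and full sample of 69 per group, and on a correlation that the documents do not supply. Only the baseline-acuity adjustment is close to free. Surgeon and astigmatism terms are optional.

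**What to change.** In section 10.2.1, for the four step-down endpoints:

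1. Pre-specify a linear model of 3-month acuity on treatment and the mean pre-operative monocular CDVA of the two eyes.
2. Take the non-inferiority limit from the adjusted treatment difference.
3. Keep the unadjusted t-test as a sensitivity analysis.
4. Optionally, where the CRF is confirmed to record the values, add corneal astigmatism for UDVA and UIVA, and surgeon if the surgeons are few. Each extra term costs a degree of freedom.
5. In section 11, state whether the blinded re-estimation uses the raw or the residual SD.

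The cost is SAP wording and a few lines of R. The baseline-acuity model needs no new data. Fix the covariates before outcomes are seen, because the trial is unmasked and a later choice could look driven by the data. Resolve the sidedness of the confidence interval as a separate amendment; adjustment is no substitute for it.

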### **10.3. General Statistical Considerations**

The statistical analyses will be performed using R, version 4.2.2 or higher. Any statistical tests of hypotheses will employ a level of significance of alpha=0.05.

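### The four monocular secondary endpoints are tested at 0.05 outside the step-down sequence, with no gate, adjustment or descriptive label (about a 9–19% chance of at least one false significant result among the four)

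*Combined protocol and SAP*

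**What the plan says.** Section 8.1 (and the summary in Section 3) names binocular CDVA at 3 months as primary and lists seven secondary outcomes. Three are binocular: UDVA, DCIVA and UIVA. Four are monocular: CDVA, UDVA, DCIVA and UIVA, for example "Monocular corrected distance visual acuity (CDVA), 3-months postop" and "Monocular uncorrected distance visual acuity (UDVA), 3-months postop". A separate list follows, introduced by "Exploratory outcome measures are as follows". It covers near acuity, defocus curves, refraction, the spectacle questionnaire, aberrations and time to release of care. The monocular acuities at distance and intermediate are not on it.

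Section 10.2.1 gives the decision rule for non-inferiority: "if the upper boundary of the 95th confidence interval is not greater than 0.1 logMAR, non-inferiority will be claimed". It then says "The step-down methodology will be used on the non-inferiority endpoints in the following order" and names binocular CDVA, DCIVA, UDVA and UIVA, and no others. The same section has a general sentence, tied to no endpoint: "Differences between parametric variables will be compared using a two-sample t-test". Section 10.3 adds: "Any statistical tests of hypotheses will employ a level of significance of alpha=0.05".

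**The concern.** The plan recognises multiplicity and handles it for the primary and three of the seven secondary endpoints. The other four have the same secondary label but no corresponding rule. Under 10.2.1 and 10.3 together, each is compared by t-test at 0.05, whatever happens in the step-down sequence.

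Suppose non-inferiority on binocular CDVA is not shown and the sequence stops at step 1. A monocular DCIVA difference with p = 0.04 could still be reported as a statistically significant result on a prespecified secondary endpoint, and nothing in the plan would tell a reader to treat it differently from a protected claim. The trial is unmasked (Section 3) and meant for publication (Section 12), so an isolated difference in favour of one lens could well be given weight.

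**Working it through.** **Inputs from the documents.** Level per test: 0.05 (Section 10.3; sidedness is not stated, two-sided is taken here for a test of difference). Secondary endpoints outside the step-down sequence: 4 (Section 8.1 set against the list in 10.2.1). All secondary endpoints: 7.

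**Input assumed.** The correlation between the test statistics. The documents give none, so a common correlation r from 0 to 0.9 is used.

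**The plan's own figure.** The documents state no family-wise error rate, so there is none to reproduce. The sample size, used below only to judge an objection, does reproduce. With margin 0.1, true difference 0.05 and SD 0.1 (Sections 10.2.1 and 11), n per group = 2 × (1.645 + 1.282)² × 0.1² / (0.1 − 0.05)² = 68.5, so 69, at one-sided 0.05 and 90% power.

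**Step 1: independent tests.** With all null hypotheses true, P(at least one false significant result) = 1 − (1 − 0.05)^k.
- k = 4 (monocular secondaries): 1 − 0.95⁴ = 18.5%
- k = 7 (all secondaries, if the binocular ones also receive difference tests): 1 − 0.95⁷ = 30.2%

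**Step 2: correlated tests.** Z_j = √r·W + √(1 − r)·e_j, with W and e_j independent standard normal. A test rejects when |Z_j| > 1.96. There were 400,000 simulated draws per cell; the r = 0 column uses the formula above.

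| Tests | r = 0 | r = 0.3 | r = 0.5 | r = 0.7 | r = 0.9 |
|---|---|---|---|---|---|
| 4 monocular secondaries | 18.5% | 17.5% | 15.5% | 13.0% | 9.3% |
| 7 secondaries | 30.2% | 27.1% | 22.9% | 17.8% | 11.4% |

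**Step 3: what the figures describe.** They are the chance of at least one false result in the family. Each test taken alone still has a 5% error rate.

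**Step 4: effect of an adjustment, if claims are wanted.** Bonferroni, or Holm's first step, for four tests uses 0.05/4 = 0.0125. Under independence the family rate is then 1 − (1 − 0.0125)⁴ = 4.9%.

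**The case against.** The strongest reply is that the confirmatory claims are already protected. The hypothesis in Section 3 concerns binocular distance vision, the objective in Section 6 is binocular outcomes, and the only rule for making a claim is the non-inferiority rule, which is ordered. No section plans a superiority claim or a monocular claim, and 10.3 sets a per-test level that is not exceeded. On this view, monocular results are supportive and need no adjustment. Much of this stands: the primary test and the sequence are not inflated. What remains is that the plan does not call these endpoints supportive. It labels other outcomes exploratory, leaves these as secondary, and gives any test a 0.05 level.

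Several stronger readings are tempting, but the documents do not carry them:

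- **A flat 15–25% false-positive chance for the secondaries.** At an assumed correlation of 0.5, four tests give 15.5% and eight give 25.1%. Joining the two mixes different families and fixes a correlation that the documents do not state. The eighth test would be binocular CDVA, which is the primary.
- **Difference tests on the binocular endpoints as a planned second set.** The t-test sentence names no endpoint and may simply be the general method behind the non-inferiority comparisons. It permits the wider reading without establishing it.
- **A true null on binocular CDVA.** Section 11 assumes a 0.05 logMAR difference. With SE = 0.1 × √(2/69) = 0.017, z is about 2.9, and a two-sided difference test at 0.05 would be significant about 84% of the time. Under the plan's own assumption, that would be a true positive.
- **Separate tests by eye.** The plan does not say whether eyes are tested separately or combined, so a larger count is conjecture.
- **A single monocular result with three times the stated error rate.** Each single result keeps 5%; only the family rate is higher.

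**Conclusion.** The gap is real and modest. Four endpoints labelled secondary can each be declared significant at 0.05 regardless of the primary result, because the plan neither gates, adjusts nor labels them. With no true difference on any of the four and two-sided tests, the chance of at least one false significant result is about 9–19%, from correlation 0.9 down to 0. If the general t-test sentence is also applied to the three binocular secondaries, the range for all seven is about 11–30%. Both ranges rest on assumed, equal correlations.

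The text does not support the inference that the trial's main conclusion is at risk: the primary non-inferiority claim and the ordered claims after it are unaffected. This is a cheap improvement to what may be concluded from the secondary results.

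**What to change.** In 10.2.1, state that confirmatory claims are limited to the four non-inferiority endpoints in the step-down sequence. State that all other between-group tests, including those on the four monocular secondary endpoints and any test of difference on a binocular endpoint, are reported as mean differences (or differences in proportions) with 95% confidence intervals and nominal p-values, without a confirmatory claim of significance.

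In 10.3, state that 0.05 is a confirmatory level only within the step-down sequence and a nominal, unadjusted level for every other test. Name the regression of monocular DCIVA on higher-order aberrations and the tests of proportions there; otherwise the change would leave them with no stated level.

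If the sponsor wants confirmatory monocular claims, test the four as a Holm-adjusted family only after step 4 (binocular UIVA) has succeeded, and first say how the two eyes of a subject enter each test.

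The cost is a few sentences, settled before outcome data are analysed. It needs no new data and leaves the primary test and the sample size unchanged. The downside is that the sponsor gives up stand-alone significance claims on the monocular endpoints.
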